Procedures. We will enroll 35 patients (20 from Aim 1 and 15 *de novo*) into this prospective single-arm cohort study to test the hypothesis that 6 months of treatment (maintenance) with etelcalcetide will decrease the propensity to calcify soft tissues as measured by T50. Similar to **Aim 1**, eligibility for enrollment into **Aim 3** will be based on a PTH level >9-times the ULN for the PTH assay (**Figure 1**), as well as their treating physician's plan to initiate etelcalcetide per standard of care. However, the presence of high turnover bone disease based on total alkaline phosphatase will not be a criterion for enrollment into **Aim 3**. Furthermore, all patients enrolled in **Aim 1** will be automatically enrolled into **Aim 3** unless they choose to opt-out of **Aim 3**. Thus, we will use the biochemical data from the 20 enrollees participating in **Aim 1** and enroll an additional 15 patients to be treated with etelcalcetide. As per **Aim 1** (**Figure 2**), after enrollment, patients will undergo a 3-month dose titration phase to ensure that PTH levels are stability maintained within the target range (300-400 pg/mL), followed by a 6-month treatment (maintenance) phase. Patients will have blood collected and stored at -80°C, at baseline (pre-treatment) and after 3- and 6-months of treatment (i.e., maintenance phase). Blood will be assayed for T50, calcium, phosphorus, PTH, vitamin D metabolites, bone formation (BSAP, P1NP) and resorption (CTX) markers, FGF-23 and sclerostin. We will assess the effect of treatment on changes in levels of T50, a clinically relevant biomarker of calcification propensity^{9, 10}. We will also determine relationships between changes in T50 and changes in phosphorus, calcium, bone turnover markers and calcitropic hormones.

Exploratory. None

Primary and Secondary Endpoints for Each Aim

Aim 1

1. Primary Endpoints: Hardness
2. Secondary Endpoints: Bone formation rate, mineralization density

Aim 2

1. Primary Endpoints: Changes in: (a) femoral neck areal BMD by DXA and (b) radius failure load by HR-pQCT
2. Secondary Endpoints: Changes in: (a) spine, total hip, and one-third and ultradistal radius BMD by DXA and (b) radius and tibia cortical density, thickness, porosity and tissue mineral density, and trabecular density, thickness, number and spacing

Aim 3

1. Primary Endpoint: Change in T50 (percent and absolute)
2. Secondary Endpoints: Changes in PTH, calcitropic hormones, FGF-23, Sclerostin, calcium and phosphorus

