Statistical methods (for analysis of primary and secondary endpoints or primary/interim analysis)

For All Aims, distributions will be examined and Anderson-Darling tests of normality and Q-Q plots will be used to guide the application of transformations to normalize the values prior to inferential testing. (Data analyzed from transformations will be reported in raw units). Inferential tests will be adjusted for multiple comparisons within a measurement domain (BMD within DXA, cortical, trabecular and FEA within HRpQCT, and each of the four compartments within histomorphometry) using a resampling, step-down procedure to control the family-wise error rate. We favor this over a false-discovery rate approach given the limited number of hypotheses within each measurement domain and that the measurement domains are traditionally seen as free to vary independently of each other^{11, 12}.

For Aim 1. A two-tailed dependent T-test of the change in hardness measured by Ramen nano-indentation and mineralization measured by histomorphometry obtained primary dynamic and secondary structural bone quality

outcome values from the pre-treatment baseline to the 6-month endpoint will be reported with an alpha-level of 5% as the criterion for statistical significance. Outcome data missing, for whatever reason, will not be imputed.

For Aim 2. A two-tailed dependent T-test of the change in femoral neck BMD by DXA and failure load measured at the distal radius by HR-pQCT from pre-treatment to the 6-month endpoint will be reported with an alpha-level of 5% as the criterion for statistical significance. Secondary endpoints include treatment differences in change in cortical density, thickness and porosity, trabecular density and thickness and spacing, and areal BMD at the forearm, spine, and total hip. Other predictors to be tested in multiple regression models of change from baseline include demographic characteristics collected in **Aim 1** and PTH, calcitropic hormones, bone formation and resorption markers, sclerostin, and FGF-23 collected in **Aim 3**. A final multiple regression model will be based on predictors that are significant in multiple regression models including baseline bone measure.

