Sample Size Justification for Aim 2. The proposed sample size of 35 participants provides >80% power and 5% alpha to detect a change in femoral neck BMD of 0.5% f and a 0.5 standard deviation change in radius failure load by HR-pQCT from pre-treatment to the 6-month endpoint. For femoral neck BMD by measured by DXA, Lien et al¹⁵ reported that in 8 patients with CKD treated with cinacalcet for 6 months, areal BMD at the femoral neck increased $2.2 \pm 1.1\%$ ($p < 0.05$). For failure load outcomes, in a longitudinal study of 29 patients with ESKD who underwent kidney transplantation, we reported that failure load decreased by $3.5 \pm 7.0\%$ ($p=0.0081$) over 12-months¹⁶; our larger sample size will permit detection of at least a 3.4% change in radius failure load due to suppression of PTH production by etelcalcetide.

Sample Size for Aim 3: N = 35 (20 from Aim 1 plus 15 additional patients)

Sample Size Justification for Aim 3: The proposed sample size of 35 participants provides >80% power and 5% alpha two-tailed dependent T-test of the change in T50 from baseline to the 6-month endpoint. Based on Smith et al¹⁰, each standard deviation (SD) decrease in T50 was associated with a 39% increase in odds of all-cause mortality. Assuming that the variability in T50 in patients on hemodialysis patients enrolled into this prospective cohort study are similar to those reported in Smith et al¹⁰, approximately 20 patients would be required to detect a 1-SD decrease in T50. Our sample size of 35 patients will permit the detection of a 0.7-SDs decline in T50. We assume that a reduction of lesser magnitude is of unclear clinical significance

Protection of Human Subjects

This study qualifies as clinical research and will be conducted in compliance with GCP and all regulatory requirements for the protection of human subjects.

Informed Consent

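### The Aim 2 predictor regression chooses its terms by significance and reports them from the same 35 patients, so ordinary p-values or intervals from it do not have their nominal properties

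*Combined protocol and SAP*

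**What the plan says.** The combined protocol and SAP, Statistical methods, For Aim 2, makes paired t-tests the primary analysis and then adds a regression analysis: "Other predictors to be tested in multiple regression models of change from baseline include demographic characteristics collected in" Aim 1, together with "PTH, calcitropic hormones, bone formation and resorption markers, sclerostin, and FGF-23" from Aim 3. The rule for the reported model is: "A final multiple regression model will be based on predictors that are significant in multiple regression models including baseline bone measure".

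The Aim 3 procedures give part of the marker list: "bone formation (BSAP, P1NP) and resorption (CTX) markers, FGF-23 and sclerostin", in addition to PTH and vitamin D metabolites. The demographic variables are not named.

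The general paragraph of Statistical methods describes a resampling step-down adjustment. Its families are groups of outcomes: BMD within DXA; cortical, trabecular and finite-element measures within HR-pQCT; and the histomorphometry compartments. Predictors are not named as a family. The plan calls some Aim 3 analyses exploratory but gives the Aim 2 regression no such label, and the line before the endpoint list records no exploratory component.

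**The concern.** A predictor reaches the final model because its estimate in these 35 patients was large relative to its standard error. Reporting it from the same patients with standard formulas ignores that filter. Chance findings then look like established determinants of response, and weak real effects look stronger than they are.

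At stake is any statement about which patients gain BMD or strength on treatment, or which marker tracks the gain. The rates below apply to each outcome modelled. Aim 2 has two primary outcomes and a long list of secondary ones, and the plan does not say which will be modelled.

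**Working it through.** **The plan's own figure.** The documents give no figure for the regression, only for the paired test that set N. Sample Size Justification for Aim 2 states more than 80% power with 35 patients for a "0.5 standard deviation change in radius failure load by HR-pQCT from pre-treatment to the 6-month endpoint". With n = 35, d = 0.5 and a two-sided 5% paired t-test (34 df), the noncentrality is 0.5 × √35 = 2.96 and the power is 82.0%. The effect detectable with 80% power is 0.487 SD. Multiplied by the cited 7.0% SD of change, this is 3.41%, in line with the stated 3.4%. N = 35 is therefore justified for the paired test of failure load. That calculation says nothing about screening predictors.

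**Inputs for the regression.**
- n = 35, from Sample Size for Aim 2.
- Laboratory candidates: BSAP, P1NP, CTX, FGF-23 and sclerostin make 5; PTH makes 6; two vitamin D metabolites (assumed, the number is not given) make 8.
- Demographics: not listed. Assuming 3-4 gives 11-12 in total.
- Selection threshold: not stated. The 5% used here is the level the plan states for its t-tests.
- Form of screening: not stated. Both readings were run: each candidate alone with baseline, and all candidates together with baseline.

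**Chance of at least one false predictor, by formula.** With k independent null candidates each tested singly, the chance is 1 − 0.95^k: 34% for k = 8 and 46% for k = 12.

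**Simulation of the rule.** No candidate has a true effect. The baseline bone measure is always in the model, terms with p<0.05 are kept, and the model is refitted on the same 35 patients. There were 3,000 runs per row, with a Monte Carlo error of about 1 point.

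| Candidates | Screening | Correlation | At least one false predictor kept | Refitted 95% interval of a kept null predictor covers zero |
|---|---|---|---|---|
| 8 | singly | 0 | 33% | 11% |
| 8 | jointly | 0 | 30% | 28% |
| 12 | singly | 0 | 46% | 18% |
| 12 | jointly | 0 | 37% | 35% |
| 12 | singly | 0.3 | 40% | 45% |
| 12 | jointly | 0.3 | 37% | 43% |

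Repeat simulations of the same design move the ends by a point or two. They give about 29-45% for the first quantity and 10-44% for the second. With 12 candidates, about 0.6 null predictors are kept per analysis.

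**Coefficient size.** The mean absolute coefficient of a kept null predictor is about 0.33-0.39 residual SD per SD of the predictor. The comparator is not zero, because a mean absolute estimate is positive even without selection. Here it is about 0.14-0.20, so selection roughly doubles it or somewhat more.

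**A real effect, 12 independent candidates, one true.**

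| True effect (residual SD per SD) | Screening | Selected in | Inflation when selected | Interval covers the true value |
|---|---|---|---|---|
| 0.3 | singly | 38% | 1.47-fold | 94% |
| 0.3 | jointly | 27% | 1.61-fold | 86% |
| 0.5 | singly | 78% | 1.06-fold | 97% |
| 0.5 | jointly | 60% | 1.19-fold | 94% |

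The coverage failure is therefore severe for null predictors and mild or absent for moderate real ones. A reader of the final model cannot tell which kind a retained term is.

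**The case against.** **The analysis is ancillary.** This stands. Predictors of response are not among the endpoints listed for Aim 2, and the sample size does not rest on them. A reader might infer that the Aim 2 result itself is compromised. The documents do not support that, because the primary tests are paired t-tests that do not use this model.

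**The inputs are assumed.** This stands too. A count of 12 candidates, the 5% threshold and the form of screening are not in the documents, and independence is doubtful for BSAP, P1NP, CTX and PTH. This is why the result is given as a range. Even its most favourable end leaves coverage for kept null predictors far below 95%.

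**The plan promises no confidence intervals for this model.** Correct. A reader might take the plan to commit to invalid intervals, but it does not. The point concerns ordinary p-values, and intervals only if they are reported.

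**Refitting is not the culprit.** Correct. With 12 candidates screened jointly, the kept null predictors averaged 0.50 in the unpruned model, where their intervals exclude zero by construction. After refitting they averaged 0.37, with 36% coverage. The significance filter causes the bias and refitting partly reduces it.

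**The chance of a false predictor is ordinary multiplicity.** Largely true. A full model with 12 null terms shows at least one p<0.05 about as often without any pruning, and four uncorrected null predictors gave 17%. What the rule adds is that the chance findings become the reported model and the remaining candidates leave it.

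**Multiplicity is already handled.** This does not stand on the text, since the step-down families are defined by outcome. Extending the procedure to predictors would limit false selections but would not restore coverage after selection.

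**Conclusion.** The point holds for the secondary Aim 2 regression and goes no further. As written, the rule selects by significance and reports on the same patients, with no correction for the selection and no exploratory label.

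Under 8-12 null candidates, p<0.05 and correlation 0 to 0.3, the false-selection rate is roughly three to more than four analyses in ten per outcome. Coverage for a kept null predictor is below one half throughout. The exact figures depend on inputs that the documents leave open; the direction does not. The sponsor should correct this before analysis, but it does not threaten the primary conclusions.

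**What to change.** 1. Replace the significance-selected final model with one small model fixed before analysis, fitted once and not pruned, for the two primary Aim 2 outcomes. It would contain the baseline bone measure and a few predictors that the sponsor names, for example age, sex and PTH. These are examples only, as the documents name no demographic variable. State whether PTH enters as baseline or as change: because patients are titrated to a common range, change in PTH may largely restate baseline PTH.
2. Report every other listed marker singly, adjusted for baseline, whether or not it is significant. Extend the step-down procedure explicitly to this set of predictors, since the present text does not cover it.
3. If a selected model is still shown, label it exploratory and give bootstrap selection frequencies, without conventional p-values or intervals.
4. List the candidates, and confirm that demographics described as collected in Aim 1 are also recorded for the 15 patients recruited de novo. Otherwise the usable n falls below 35.

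The cost is SAP wording and slightly different code, with no new data or visits. The downside is that fewer predictors are considered jointly. The small model is not free of chance findings: three independent null predictors give 1 − 0.95³ = 14% for at least one p<0.05. But all its terms are reported, so under the usual regression assumptions its intervals keep their nominal coverage.

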For Aim 3. A two-tailed dependent T-test of the change in primary calcification propensity (T50) and secondary biochemical indices (calcitropic hormones, FGF-23, sclerostin, calcium and phosphorus) from pre-treatment baseline to the 6-month endpoint will be reported with an alpha-level of 5% as the criterion for statistical significance. Secondary exploratory analyses will assess the within-subject temporal course of change in the biochemical outcome with linear mixed models for repeated measures with time as a fixed effect (0, 3 and 6 months); the baseline value of the dependent variable entered as a continuous covariate; and a covariance structure determined by empirical testing performed prior to inferential testing. We will also assess whether the **Aim 1** participants differ from the patients recruited *de novo* for **Aim 3** with an independent T-test both of the two groups' baseline values and of the two groups' change in values from baseline to the 6-month endpoint. We will explore the covariances between changes in T50 and other biochemical markers of bone turnover and calcitropic hormones with simple and multiple regression with synchronized and lagged observations in time to determine whether leading, cotemporaneous or following patterns exist among these measures.

Subject Recruitment and Selection

Study site and number of patients eligible for enrollment. ESKD patients receiving hemodialysis at the Rogosin Institute, meeting enrollment criteria, and whose treating physicians intend to initiate treatment with etelcalcetide will be asked to participate in this study. Rogosin is the largest provider of hemodialysis in New York City and provides hemodialysis services to over 1300 patients. Approximately 25% of patients at Rogosin have PTH levels > 9-times the ULN for the PTH assay. Therefore, there are adequate numbers of patients at Rogosin who may be able and willing to participate in this prospective cohort study.

Enrollment Criteria

Inclusion criteria

For All Aims:

1. Patient has provided informed consent.
2. Patient is 18 years of age or older.
3. Patient must be receiving maintenance hemodialysis for at least 3 months, with adequate hemodialysis with a delivered Kt/V 1.2 or urea reduction ratio (URR) 65% within 4 weeks prior to screening laboratory assessments.
4. Dialysate calcium concentration must be stable for at least 4 weeks prior to screening laboratory assessments.

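### The Aim 3 primary paired t-test drops patients without a final T50 and leaves their intermediate T50 unused; if loss is related to T50, the single-arm change is biased in a direction the documents do not determine

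*Combined protocol and SAP*

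**What the plan says.** **Primary test.** Statistical methods, For Aim 3, specifies "A two-tailed dependent T-test of the change in primary calcification propensity (T50", from baseline to the 6-month endpoint, and the result "will be reported with an alpha-level of 5% as the criterion for statistical significance". A paired test needs both values from each patient.

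**Draws.** The Aim 3 procedures take T50 three times: before treatment and after 3 and 6 months of maintenance. Table 1 labels the two later visits 3 and 9 months.

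**Use of the intermediate draw.** It enters analyses labelled secondary and exploratory: "linear mixed models for repeated measures with time as a fixed effect (0, 3 and 6 months", with the baseline value also entered as a covariate, and regressions of T50 change on other markers with lagged observations. It has no part in the primary test.

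**Missing data.** Aim 3 states no missing-data rule, analysis population or sensitivity analysis. The one sentence on the subject, "Outcome data missing, for whatever reason, will not be imputed", is in the For Aim 1 paragraph and is not an Aim 3 rule. The Early Study Cessation Clause covers transplant only: after at least 3 months on drug, end-of-study procedures done within 4 weeks after transplant count in the final analysis.

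**Sample size.** "Sample Size for Aim 3: N = 35 (20 from Aim 1 plus 15 additional patients"; this number "provides >80% power and 5% alpha two-tailed dependent T-test of the change in T50". No dropout rate is given.

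**The concern.** Follow-up lasts about 9 months (3 of titration, 6 of maintenance) in hemodialysis patients with severe hyperparathyroidism, so some final draws may be missing. The paired test then estimates the change among completers only. If those who leave differ in T50 change from those who stay, the completer mean differs from the mean for all 35. There is no control arm, so this difference cannot be separated from a drug effect. The intermediate T50 could correct part of it, and the plan collects that value but does not use it in the primary analysis. At stake is the estimated T50 change and the error rate of the Aim 3 primary test.

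**Working it through.** **1. The plan's own figure.** With SD of change = SD(T50) x sqrt(2(1 - r)) and within-patient correlation r = 0, the SD of change is 1.414 SD. A 0.7-SD change is then 0.7/1.414 = 0.495 SDs of change, and the noncentrality is 0.495 x sqrt(35) = 2.93. Exact power (two-sided 5%, 34 df) is 81.2%, and 35 is the smallest N reaching 80%. This reproduces "Our sample size of 35 patients will permit the detection of a 0.7-SDs decline in T50". For 1 SD the same method gives N = 18, close to the plan's "approximately 20 patients would be required to detect a 1-SD decrease in T50". On this basis there is no dropout margin: with 20% lost (28 pairs), noncentrality is 0.495 x sqrt(28) = 2.62 and power is 71.4%. If 0.7 SD means SDs of change, power is 98.0% with 35 pairs and 94.6% with 28.

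**2. Set-up for the bias.** Everything here is assumed; the documents give no dropout rate, no reasons and no correlation. N = 35, T50 in SD units, correlation 0.6 between visits. Loss occurs after the intermediate draw, with log-odds changing by 1 per SD of the intermediate change. Benefit means a rise in T50. The comparator is a maximum-likelihood estimate using all three draws.

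**3. Results.** Bias is the mean estimate minus the true change. False benefit is the proportion of trials in which the completer test declares benefit when there is no true change (nominal 2.5%).

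| Loss; correlation of last two draws | Completer bias, poor responders leave | Completer bias, good responders leave | False benefit, poor responders leave | All-draw likelihood bias |
|---|---|---|---|---|
| 5%; 0.6 | about +0.02 | about -0.02 | about 3% | about 0 |
| 15%; 0.6 | +0.055 | about -0.05 | about 5% | about 0 |
| 25%; 0.6 | +0.09 | -0.09 | about 7% | about 0 |
| 25%; 0.8 | +0.13 | -0.13 | about 12% | about 0 |

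Against a true change of 0.50 SD, the three larger positive biases are 0.055/0.50 = 11%, 0.09/0.50 = 18% and 0.13/0.50 = 26%. With purely random loss of 15-25%, both estimates are unbiased and the likelihood estimate is 4-17% more efficient.

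**4. Check by arithmetic.** The variance of the intermediate change is 2(1 - 0.6) = 0.8. Its covariance with the final change is 1 - 0.6 - 0.6 + c, where c is the correlation of the last two draws. The slope of final on intermediate change is therefore 0.4/0.8 = 0.5 for c = 0.6, and 0.6/0.8 = 0.75 for c = 0.8. At 25% loss, selection shifts the completers' mean of the driving change by 0.177 SD. So the bias is 0.5 x 0.177 = 0.09 or 0.75 x 0.177 = 0.13, as simulated.

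**5. Where the likelihood model falls short** (25% lost, correlation 0.6):
- All leavers lost before the intermediate draw: 0.055 of 0.088 SD remains (62%).
- Loss driven by the unseen final change: 0.127 of 0.177 SD remains (72%).

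**6. Other assumed settings.** With a steeper slope (1.5 per SD of change), 10-30% lost and correlation 0.3-0.7, completer bias is 0.05-0.19 SD in either direction when loss follows the intermediate change. If poor responders leave, two-sided type I error is then 6-12%. Likelihood bias stays near zero.

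**The case against.** A reader might infer that the completer analysis must flatter the drug, because patients who do badly leave. The documents do not support that.

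- They give no dropout rate, no reasons and no T50 for leavers. Doing badly clinically is not the same as having a poor T50 change.
- The protocol's Hypotheses section expects lower serum calcium to reduce calcification propensity. On that hypothesis a patient lost through hypocalcemia would tend to have a favourable T50, and the loss would bias against benefit.
- Many foreseeable events need not cost a final draw. The hypocalcemia section describes holding the drug, monitoring and restarting, not ending follow-up. The exclusion criteria remove anticipated or scheduled parathyroidectomy, unstable patients and those unlikely to complete visits. Blood comes from the dialysis line. Some transplant patients are kept in.
- If loss is unrelated to T50, the paired t-test is valid and only modestly inefficient.
- The set-up in steps 2 and 3 suits the likelihood model, since loss depends only on observed values. Step 5 shows how much remains otherwise.

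All of this stands, and it removes any claim of a fixed direction or a known size. It does not remove the gap: the primary test cannot use a patient without the final draw, the intermediate T50 goes unused there, and Aim 3 says nothing about missing data. Nor does the fix depend on the direction; the likelihood estimate is about unbiased whichever responders leave, provided observed T50 explains the loss.

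**Conclusion.** The point holds without a direction. The Aim 3 primary test discards any patient without a final T50, together with that patient's intermediate value. Loss related to T50 would bias the single-arm change, and the documents do not settle the sign. The size is about 0.05-0.13 SD either way for 15-25% loss after the intermediate draw, and about 0.02 SD at 5%; it is zero under random loss, at a cost of about 4-17% in efficiency. These figures rest on assumed correlations, loss rates and dropout slopes.

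Two further readings go too far. The plan as a whole does not ignore the intermediate T50; it uses it in exploratory models. The no-imputation sentence belongs to Aim 1 and is not evidence of an Aim 3 rule.

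**What to change.** 1. Make the primary Aim 3 analysis a likelihood-based repeated-measures model on all T50 draws of all 35 patients, with categorical visit, unstructured covariance and Kenward-Roger degrees of freedom. The primary contrast is endpoint minus baseline.
2. Enter baseline as one of the three responses and not also as a covariate. The exploratory model as written does both.
3. State the missing-data assumption for Aim 3, keep the paired t-test as a sensitivity analysis, and tabulate the reason for each missing endpoint draw. The reasons will show which direction of bias is plausible.
4. State which visit an early post-transplant draw is assigned to.
5. Reconcile the visit timing between Table 1 (3 and 9 months) and the text (3 and 6 months of maintenance). It decides how far the intermediate draw is from the endpoint, and so how much it can inform a missing final value.
6. Reconcile the sign. The sample-size text targets a decline in T50, while the mortality association it cites makes a decline unfavourable.

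The cost is SAP wording; no new draws are needed. It is a respecification, though, not simply a promotion of the planned model, which has baseline as a covariate and an empirically chosen covariance. With no missing draws it gives essentially the paired t-test. The downside to state in the SAP is that the model assumes loss is explained by observed T50, corrects little for patients lost before the intermediate draw, and corrects only part of the bias if loss depends on the unseen final value.
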